#### 4.3.2 Pralatrexate

##### Overview

Pralatrexate is presently approved for the treatment of relapsed or refractory PTCL. [name] et al in the pivotal study PROPEL showed that pralatrexate produced an overall response rate of 29% and a median duration of response of 10.4 months in a heavily pretreated group of patients. Pralatrexate is a novel antifolate that has been rationally designed to have increased affinity for the reduced folate carrier (RFC-1), allowing for better internalization into the cell. Pralatrexate is also a better substrate for polyglutamation by FPGS (folylpolyglutamyl synthetase) allowing for better retention in the cell compared to MTX. In addition, the polyglutamate chains formed by pralatrexate tend to be longer than those formed on MTX, which appears to improve the inhibition of the target enzyme dihydrofolate reductase (DHFR). Collectively, these pharmacological attributes render pralatrexate a more potent cytotoxic agent *in vitro* and *in vivo* compared to MTX across a broad panel of lymphoma cell lines. Clinical trials to assess the efficacy of pralatrexate in other forms of lymphoma are ongoing including CTCL and B-cell malignancies. Interestingly, initial clinical experiences seemed to suggest that pralatrexate was more active in T- over B-cell lymphomas, though; admittedly few patients with B-cell lymphoma have been treated. Dedicated studies exploring the activity of pralatrexate in B-cell neoplasms on a weekly schedule are now ongoing. Some data has suggested that the activity in different lymphoid neoplasms may correlate with higher levels of RFC-1 in sensitive cells, suggesting that RFC-1 could be an important biomarker of activity. While many laboratory studies are now ongoing to explore these relationships, it is clear that any up-regulation of RFC-1 could lead to marked improvement in the activity of pralatrexate. Such pharmacologic strategies could lead to the generation of rational synergistic combinations.

The regulation of RFC-1 is complex. The promoter site of RFC is known to be epigenetically regulated and known to be hypermethylated in many tumor types. This observation has led to the hypothesis that RFC expression can be pharmacologically modulated by histone deacetylase inhibitors and hypomethylating

agents, both of which are known to influence the epigenetic regulation of many genes. These biological features of RFC regulation suggest that rational combinations of select agents known (or suspected of regulating RFC expression) may provide a basis for exploring the potential synergistic combinations of pralatrexate and HDACI or hypomethylating agents.

### **Mechanism of Action**

Pralatrexate is a unique antifolate that has been rationally designed to have a high affinity for the reduced folate receptor (RFC-1) and the enzyme folylpolyglutamyl synthetase . This allows the drug to be selectively accumulated in tumor cells. RFC expression is induced by various oncogenes, including *H-ras* and *c-myc*, which results in an increase in the rate of internalization of radio-labeled antifolate. Several studies have shown greater cytotoxic properties for pralatrexate compared to methotrexate, but its precise mechanism of action and T-cell specificity remain objects of research. Preliminary gene expression profiling and pathway analysis comparing methotrexate and pralatrexate demonstrated that pralatrexate specifically affects immune response signaling, cytokine production and lymphocyte activation pathways.

### **Clinical Pharmacokinetics**

Non-compartmental and population PK (POPPK) analyses showed that pralatrexate *R* and *S* diastereomers follow apparent first-order PK with the area under the curve to infinity (AUC $\infty$ ) increasing in a near linear manner with dose. Total, renal, and non-renal clearance as well as volume of distribution were constant within (nominal) doses ranging from 30 mg/m^2 to 325 mg/m^2. Comparing the 2 diastereomers, plasma exposures of the *R* diastereomer exceed those of the *S* diastereomer by approximately 2-fold; the reason for this is unclear at this point. *S* and *R* diastereomer clearance were reduced by 0.128 and 0.0778 L/hour per 1 mL/min reduction in creatinine clearance for patients with a creatinine clearance less than 80 mL/min. Although the estimated effects of creatinine clearance appeared to be clinically insignificant, few patients with moderate to severe renal impairment were enrolled in these studies, making characterization of the effects of renal impairment on pralatrexate disposition difficult. Based on clearance parameters, it appears that renal tubular and hepatobiliary drug transporters may play an important role in the elimination of pralatrexate.

In vitro plasma protein binding studies showed that pralatrexate was 67-86% bound to human plasma protein, with human serum albumin being a significant contributor to the total binding. Pralatrexate did not compete with plasma protein binding of 6 drugs that were selected as reference compounds for different plasma protein binding sites. These studies suggest that pralatrexate at clinically relevant concentrations is not likely to cause displacement of other drugs from plasma proteins. Of note is that the reciprocal study also showed that 6 selected reference agents did not displace pralatrexate from plasma proteins. These results collectively suggest that a plasma protein binding displacement drug interaction is unlikely.

### **Safety**

The most frequent AEs, regardless of causality, reported in single-agent studies of hematologic malignancies were fatigue (n=86, 47%), nausea (n=74, 41%), mucosal inflammation (n=67, 37%), stomatitis (n=66, 36%), and constipation (n=65, 36%).

Patients with ATLL and HTLV-1 will be closely monitored by both the principle investigator and the DSMB.

Patients receiving pralatrexate should be monitored closely because AEs may occur at any time during therapy. For detailed information about the safety profile of pralatrexate, refer to the current pralatrexate IB and/or package insert.

### **Efficacy in Non-Hodgkin's Lymphoma**

Pralatrexate is FDA approved for the treatment of PTCL. There are data published by our group that suggest that pralatrexate is strongly synergistic in combination with bortezomib and other agents including romidepsin and hypomethylating agents in the treatment of PTCLs. Pralatrexate used in combination with romidepsin and hypomethylating agents represent a novel and potentially important platform for the

treatment of T-cell malignancies. Early clinical phase I/II trials exploring the value of the doublet combination of pralatrexate plus romidepsin and azacytidine plus romidepsin are currently ongoing with very promising results.

#### 4.3.3 Decitabine

Decitabine (5-aza-2'-deoxycytidine) is a hypomethylating agent thought to exert its antineoplastic effects after phosphorylation and direct incorporation into DNA. This process leads to DNA methyltransferase irreversible inhibition, causing hypomethylation of DNA and resulting in cellular differentiation or apoptosis. Decitabine inhibits DNA methylation *in vitro*, which is achieved at concentrations that do not cause major suppression of DNA synthesis. Decitabine-induced hypomethylation in neoplastic cells may restore normal function to genes that are critical for the control of cellular differentiation and proliferation. In rapidly dividing cells, the cytotoxicity of decitabine may also be attributed to the formation of covalent adducts between DNA methyltransferase and decitabine incorporated into DNA. Nonproliferating cells are relatively insensitive to decitabine.

#### Mechanism of Action of Decitabine

Decitabine is believed to exert its antineoplastic effects after phosphorylation and direct incorporation into DNA and inhibition of DNA methyltransferase, causing hypomethylation of DNA and cellular differentiation or apoptosis. Decitabine inhibits DNA methylation *in vitro*, which is achieved at concentrations that do not cause major suppression of DNA synthesis. Decitabine-induced hypomethylation in neoplastic cells may restore normal function to genes that are critical for the control of cellular differentiation and proliferation. In rapidly dividing cells, the cytotoxicity of decitabine may also be attributed to the formation of covalent adducts between DNA methyltransferase and decitabine incorporated into DNA. Non-proliferating cells are relatively insensitive to decitabine.

#### Nonclinical Pharmacology of Decitabine - pharmacodynamics and pharmacokinetics

Decitabine has been shown to induce hypomethylation both *in vitro* and *in vivo*. However, there have been no studies of decitabine-induced hypomethylation and pharmacokinetic parameters. Pharmacokinetic parameters were evaluated in patients. Eleven patients received 20 mg/m^2 infused over 1 hour intravenously (treatment Option 2). Fourteen patients received 15 mg/m^2 infused over 3 hours (treatment Option 1). PK parameters are shown in Table 3. Plasma concentration-time profiles after discontinuation of infusion showed a biexponential decline. The CL of decitabine was higher following treatment Option 2. Upon repeat doses there was no systemic accumulation of decitabine or any changes in PK parameters. Population PK analysis (N=35) showed that the cumulative AUC per cycle for treatment Option 2 was 2.3.2. The exact route of elimination and metabolic fate of decitabine is not known in humans. One of the pathways of elimination of decitabine appears to be deamination by cytidine deaminase found principally in the liver but also in granulocytes, intestinal epithelium and whole blood.

#### Nonclinical Toxicology of Decitabine

Carcinogenicity studies with decitabine have not been conducted. The mutagenic potential of decitabine was tested in several *in vitro* and *in vivo* systems. Decitabine increased mutation frequency in L5178Y mouse lymphoma cells, and mutations were produced in an *Escherichia coli lac-I* transgene in colonic DNA of decitabine-treated mice. Decitabine caused chromosomal rearrangements in larvae of fruit flies. The effect of decitabine on postnatal development and reproductive capacity was evaluated in mice administered a single 3 mg/m^2 IP injection (approximately 7% the recommended daily clinical dose) on day 10 of gestation. Body weights of males and females exposed *in utero* to decitabine were significantly reduced relative to controls at all postnatal time points. No consistent effect on fertility was seen when female mice exposed *in utero* were mated to untreated males. Untreated females mated to males exposed *in utero* showed decreased fertility at 3 and 5 months of age (36% and 0% pregnancy rate, respectively). In male mice given IP injections of 0.15, 0.3 or 0.45 mg/m^2 decitabine (approximately 0.3% to 1% the recommended clinical

dose) 3 times a week for 7 weeks, decitabine did not affect survival, body weight gain or hematological measures (hemoglobin and WBC counts). Testes weights were reduced, abnormal histology was observed and significant decreases in sperm number were found at doses  $\geq 0.3$  mg/m^2. In females mated to males dosed with  $\geq 0.3$  mg/m^2 decitabine, pregnancy rate was reduced, and preimplantation loss was significantly increased.

### **Safety of Decitabine**

Most common adverse reactions (>50%) are neutropenia, thrombocytopenia, anemia, and pyrexia. Following the first cycle of DACOGEN treatment, if any of the following non-hematologic toxicities are present, DACOGEN treatment should not be restarted until the toxicity is resolved: 1) serum creatinine  $\geq 2$  mg/dL; 2) SGPT, total bilirubin  $\geq 2$  times ULN; 3) and active or uncontrolled infection.

### **Efficacy of Decitabine**

A randomized open-label, multicenter, controlled trial evaluated 170 adult patients with myelodysplastic syndromes (MDS) meeting French American-British (FAB) classification criteria and International Prognostic Scoring System (IPSS) High-Risk, Intermediate-2 and Intermediate-1 prognostic scores. Eighty-nine patients were randomized to DACOGEN therapy plus supportive care (only 83 received DACOGEN), and 81 to Supportive Care (SC) alone. Patients with Acute Myeloid Leukemia (AML) were not intended to be included. Of the 170 patients included in the study, independent review (adjudicated diagnosis) found that 12 patients (9 in the DACOGEN arm and 3 in the SC arm) had the diagnosis of AML at baseline. Baseline demographics and other patient characteristics in the Intent-to-Treat (ITT) population were similar between the 2 groups. Patients randomized to the DACOGEN arm received DACOGEN intravenously infused at a dose of 15 mg/m^2 over a 3-hour period, every 8 hours, for 3 consecutive days. This cycle was repeated every 6 weeks, depending on the patient's clinical response and toxicity. Supportive care consisted of blood and blood product transfusions, prophylactic antibiotics, and hematopoietic growth factors. The study endpoints were overall response rate (complete response + partial response) and time to AML or death. Responses were classified using the MDS International Working Group (IWG) criteria; patients were required to be RBC and platelet transfusion independent during the time of response. The overall response rate (CR+PR) in the ITT population was 17% in DACOGEN-treated patients and 0% in the SC group ( $p < 0.001$ ). The overall response rate was 21% (12/56) in DACOGEN-treated patients considered evaluable for response (i.e., those patients with pathologically confirmed MDS at baseline who received at least 2 cycles of treatment). The median duration of response (range) for patients who responded to DACOGEN was 288 days (116-388) and median time to response (range) was 93 days (55-272). All but one of the DACOGEN-treated patients who responded did so by the fourth cycle. Benefit was seen in an additional 13% of DACOGEN-treated patients who had hematologic improvement, defined as a response less than PR lasting at least 8 weeks, compared to 7% of SC patients. DACOGEN treatment did not significantly delay the median time to AML or death versus supportive care. All patients with a CR or PR were RBC and platelet transfusion independent in the absence of growth factors. Responses occurred in patients with an adjudicated baseline diagnosis of AML.

## **5.0 TREATMENT PLAN**

### **5.1 Study Design**

[figure not shown]
In Arm A and Arm C, because there are non-overlapping toxicities between pralatrexate or decitabine and pembrolizumab, a classic 3 x 3 dose escalation design will not be applied. Rather, in Arm A and Arm C, we will start at the known MTD for each drug and use a CRM design for dose escalation and de-escalation. In Arm B, a CRM design for escalation of more than one agent (POCRM) will be applied.

Pralatrexate and decitabine will be administered as described every 28 days (Q4W).

Pembrolizumab will be administered at the fixed dose of 200 mg every 3 weeks (Q3W) based on simulations performed using the population PK model of pembrolizumab showing that the fixed dose of 200 mg every 3 weeks will provide exposures that: (1) are optimally consistent with those obtained with the 2 mg/kg dose every 3 weeks; (2) will maintain individual patient exposures in the exposure range established in melanoma as associated with maximal efficacy response and, (3) will maintain individual patient exposure in the exposure range established in melanoma that are well tolerated and safe. As noted above, the different drugs used in this trial will be administered following different schedule, every 3 weeks (Q3W) for pembrolizumab and every 4 weeks (Q4W) for pralatrexate and decitabine. Each cycle is 28 days. The trial schema for the first 12 weeks of treatment is provided below.

Participants will be enrolled only onto Arms A and C until the required number of patients are accrued to both arms. Enrollment onto Arm A or Arm C will be based on investigators' choice. Once enrollment onto Arm A or Arm C is completed, the next participant(s) will be assigned to the open Arm (A or C). Arm B will be the last Arm enrolling patients as important toxicity information could be learned from treating patients on the doublet combinations in Arm A and Arm C.

### TRIAL SCHEMA

### 5.2 Agents Administration

Details regarding study drug administrations are reported in the sections below (Section 5.2.1, Section 5.2.2 and Section 5.2.3). Dose modifications are detailed in Section 7.3.

Refer to FDA approved package insert and//or investigator's brochure for each study drug for anything not specifically mentioned in the protocol.

### **5.2.1 Pembrolizumab**

Pembrolizumab will be administered at the fixed dose of 200 mg every 3 weeks (Q3W) in all the study arms. In Arm A, pembrolizumab will be started on day 1 of cycle 1. In Arm B and Arm C, pembrolizumab administration will be started on day 8 of cycle 1 to allow respectively sensitization with pralatrexate and decitabine.

### **5.2.2 Pralatrexate**

In Arm A, pralatrexate will be administered at the entry dose of  $30 \text{ mg/m}^2$  day 1, 8, 15 Q4W which represents the MTD identified in the PROPEL trial. Allocation of participants to doses of Pralatrexate will be conducted according to the study design described in [Section 10: Statistical Considerations](#).

In Arm B, pralatrexate will be administered at the entry dose of  $20 \text{ mg/m}^2$  day 1, 8, 15 Q4W and subsequently de-escalated (if applicable) following the study design described in the Statistical Considerations.

All patients receiving pralatrexate will receive folic acid at the dose of 1,000 mg orally daily and vitamin B12 intramuscularly every 2 cycles (8 weeks) as recommended in the package insert of the product. The vitamin supplementation will start prior to the first dose of pralatrexate as recommended in the drug package insert. Leucovorin will be used to decrease the risk of mucositis in all patients receiving treatment with pralatrexate. Leucovorin will be given at the dose of 15 mg orally twice daily and should be held the day before, the day of and the day after pralatrexate treatment. Leucovorin is mandatory for patients on trial.

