## 6.2 Trial Treatments

The treatment arms to be used in this trial are outlined in Table 7, Table 8 and Table 9 below.

Table 7: Trial Treatment – Arm A

Agent	Premedication Precautions	Dose	Route	Schedule A	Cycle Length
Pembrolizumab	N/A	200 mg (flat dose)	IV Administered first during cycle 1	Days 1*	Q3W
Pralatrexate	B12 and Folate supplementation (to be started within one week before initiation of treatment), and leucovorin (LV) as outlined	20 or 30 mg/m  **	IV push	Days 1, 8, 15	Q4W

\*Day 1 for pembrolizumab administration refers only to cycle 1 of treatment. Pembrolizumab will be continued every 3 weeks following the first administration.

\*\* Doses as appropriate for assigned dose level. Pralatrexate dose will be calculated using weight at cycle 1 day 1, unless weight has changed more than 10%. If so, the total dose should be calculated on the updated weight.

Table 8: Trial Treatment – Arm B

Agent	Premedication Precautions	Dose	Route	Schedule B	Cycle Length
Decitabine	Antiemetic	10 mg/m  *	IV	Days 1, 2,3,4,5	Q4W
Pralatrexate	B12 and Folate supplementation (to be started within one week before initiation of treatment) and leucovorin (LV)	20 mg/m  *	IV push	Days 1,8,15	
Pembrolizumab	N/A	200 mg (Flat dose)	IV	Day 8**	Q3W

\* Doses as appropriate for assigned dose level. Pralatrexate and decitabine dose will be calculated using weight at cycle 1 day 1, unless weight has changed more than 10%. If so, the total dose should be calculated on the updated weight.

\*\*Day 8 for pembrolizumab administration refers only to cycle 1 of treatment. Pembrolizumab will be continued every 3 weeks following the first administration.

Table 9: Trial Treatment – Arm C

Agent	Premedication Precautions	Dose	Route	Schedule C	Cycle Length
Pembrolizumab	N/A	200 mg (flat dose)	IV (Administered first during cycle 1)	Days 8*	Q3W
Decitabine	Antiemetic	20 mg/m  **	IV	Days 1,2, 3, 4, 5	Q4W

*\*Day 8 for pembrolizumab administration refer only to cycle 1 of treatment. Pembrolizumab will be continued every 3 weeks following the first administration.*

*\*\*Doses as appropriate for assigned dose level. Decitabine dose will be calculated using weight at cycle 1 day 1, unless weight has changed more than 10%. If so, the total dose should be calculated on the updated weight.*

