## 7.8 Rescue Medications & Supportive Care

### 7.8.1 Prophylactic Measurements and Supportive Care

Patients will be permitted to receive appropriate supportive care measures as deemed necessary by the treating physician including but not limited to the items outlined below:

- **Diarrhea:** Diarrhea should be treated promptly as it could represent an immune-related adverse event due to pembrolizumab administration. Please follow section 7.8.2 for supportive care guidelines for immune-related adverse events in case of diarrhea.
- **Nausea/vomiting:** Nausea and vomiting should be treated aggressively, with agents such as prochlorperazine, metoclopramide, 5-HT-3 inhibitors, or benzodiazepines. Patients should be strongly encouraged to maintain liberal oral fluid intake during therapy, especially during the initial 14 days of each treatment cycle.
- **Fatigue:** May be cumulative with increasing cycles of therapy. Can be treated as recommended in the NCCN Guidelines 2017 available online.
- **Anemia:** Transfusions or erythropoietin may be utilized as clinically indicated for the treatment of symptomatic anemia but should be clearly noted as concurrent medications.
- **Thrombocytopenia:** Transfusion of platelets may be used if clinically indicated. Dose modification for thrombocytopenia is allowed. Prophylactic folic acid and vitamin B12 supplements may be necessary to reduce hematologic toxicity as indicated in section and should be used as detailed in section 5.2.2.
- **Neutropenia:** Prophylactic use of colony-stimulating factors including granulocyte colony stimulating factor (G-CSF), pegylated G-CSF or granulocyte-macrophage colony stimulating factor (GM-CSF) may be utilized if clinically indicated and as suggested in Table 12 and Table 13.
- **Hypokalemia or hypomagnesemia** should be corrected prior to administration of study drugs, and consideration should be given to monitoring potassium and magnesium in patients experiencing side effects potentially affecting serum electrolytes (e.g. patients with nausea, vomiting, diarrhea, fluid imbalance or cardiac symptoms.)
- **Oral Mucositis:** Pralatrexate may cause mucositis, including stomatitis or mucosal inflammation of gastrointestinal and genitourinary tracts; prophylactic folic acid and vitamin B12 supplements are necessary to reduce treatment-related mucositis; dosage modification may be required. Please see section 5.2.2 and the FDA approved package insert for any clarification.

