## **9.0 TRIAL PROCEDURES**

### **9.1 Trial Procedures**

The Trial Flow Chart - Section 8.0 summarizes the trial procedures to be performed at each visit. Individual trial procedures are described in detail below. Study treatment is expected up to two years. It may be necessary to perform these procedures at unscheduled time points if deemed clinically necessary by the investigator.

Furthermore, additional evaluations/testing may be deemed necessary by the Sponsor and/or Merck for reasons related to subject safety. In some cases, such evaluation/testing may be potentially sensitive in nature (e.g., HIV, Hepatitis C, etc.), and thus local regulations may require that additional informed consent be obtained from the subject. In these cases, such evaluations/testing will be performed in accordance with those regulations.

Data collection is the responsibility of the clinical trial staff at the site under the supervision of the site investigator. The investigator is responsible for ensuring the accuracy, completeness, legibility, and timeliness of the data reported.

All source documents should be completed in a neat, legible manner to ensure accurate interpretation of data.

Clinical data (including adverse events (AEs), concomitant medications, and expected adverse reactions data) and clinical laboratory data will be entered into Forte EDC, a password-protected data capture system provided by the UVA Coordinating Center / GTcLC. Clinical data will be entered directly from the source documents.

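### Folic acid is ordered at 1,000 mg (1 g) by mouth daily for every pralatrexate recipient, probably a unit error, to be checked against the package insert

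*Protocol*

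**What the plan says.** Section 5.2.2 of the protocol states: "All patients receiving pralatrexate will receive folic acid at the dose of 1,000 mg orally daily". The same sentence adds vitamin B12, "intramuscularly every 2 cycles (8 weeks) as recommended in the package insert of the product". Section 6.2 repeats the folic acid order below the treatment tables, with the same number, unit and attribution.

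Other references to folate give no dose:

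- Tables 7 and 8 in Section 6.2 list only "B12 and Folate supplementation (to be started within one week before initiation of treatment" as a precaution for pralatrexate.
- The thrombocytopenia item in Section 7.8.1 says folic acid and B12 may be needed "as indicated in section and should be used as detailed in section 5.2.2".
- The oral mucositis item in Section 7.8.1 says: "Please see section 5.2.2 and the FDA approved package insert for any clarification".

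For leucovorin, Section 5.2.2 says: "Leucovorin will be given at the dose of 15 mg orally twice daily and should be held the day before", and the hold also covers the day of pralatrexate and the day after. No such hold is stated for folic acid.

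**The concern.** Section 7.8.1 describes folic acid here as a prophylactic supplement to limit mucositis and hematologic toxicity. Section 4.3.2 describes pralatrexate as an antifolate, and Sections 5.2.2 and 6.2 dose it at 20 or 30 mg/m² on up to three days per cycle. A gram of folic acid every day, continued through the pralatrexate days, is out of scale with that purpose and with the other doses in the same section. The figure reads like a unit slip.

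It sits in the treatment sections as a prescribing instruction, so a wrong number or unit is a patient-safety matter. Because the text says the regimen is "as recommended in the package insert of the product", a site that finds a different figure in the insert would hold two conflicting instructions. Section 5.2 sends sites to the insert or investigator's brochure only for matters the protocol does not itself cover. Folic acid is covered, so the printed figure would stand.

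The order is still live. Section 10.4 allows up to 5 more participants in Arm A and up to 26 more in Arm B, all of whom receive pralatrexate. Section 9.1 adds: "Study treatment is expected up to two years".

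**Working it through.** The protocol gives no calculation to reproduce. The check compares the printed doses over one 28-day cycle.

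**Inputs**

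- Folic acid: 1,000 mg daily, no hold stated (Sections 5.2.2 and 6.2).
- Leucovorin: 15 mg twice daily, held the day before, of and after pralatrexate (Section 5.2.2).
- Pralatrexate days: 1, 8, 15 or 1, 15, depending on dose level (Section 10.1).
- Cycle length: 28 days (Section 5.1).

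**Folic acid per cycle, as printed**

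1,000 mg × 28 = 28,000 mg = 28 g.

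**Leucovorin per cycle, as printed**

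Daily dose: 2 × 15 = 30 mg. On a daily basis, printed folic acid is 1,000 / 30 = 33 times this.

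| Pralatrexate days | Days leucovorin is held | Days given | Leucovorin total | Folic acid ÷ leucovorin |
|---|---|---|---|---|
| 1, 8, 15 | 28 (previous cycle), 1, 2, 7, 8, 9, 14, 15, 16 = 9 | 19 | 19 × 30 = 570 mg | 28,000 / 570 = 49.1 |
| 1, 15 | 28 (previous cycle), 1, 2, 14, 15, 16 = 6 | 22 | 22 × 30 = 660 mg | 28,000 / 660 = 42.4 |

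These ratios show scale only. The protocol states no dose equivalence between folic acid and leucovorin.

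**If micrograms were intended (an assumption)**

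1,000 mcg = 1 mg per day, and 1 mg × 28 = 28 mg per cycle. The printed order would then be 28,000 / 28 = 1,000 times too high.

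**Could this be a fault in reading the PDF?**

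Unlikely. The same number and unit appear in two sections whose surrounding leucovorin sentences differ, and micro-units are preserved elsewhere: µL in Section 5.4, mcL in Table 6 and µL in Table 12.

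**The case against.** The strongest objection is that the documents cannot prove the dose wrong. No section gives a usual or maximum folic acid dose, or any microgram figure, and the one source that would settle it, the insert, is not at hand. Leucovorin is a different compound, so the ratios do not establish an error. A missing hold for folic acid is not in itself a sign of one. The 1,000-fold figure follows only if micrograms were meant. All of this stands, and it limits the point to a probable error that needs verification.

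The leucovorin totals also assume continuous use. Section 5.2.2 makes leucovorin mandatory, but Section 6.2 words it conditionally, as a rescue measure. Rescue-only use would lower the leucovorin total and widen the gap, so this does not weaken the comparison.

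A further objection is that the text already points to the insert. The order cites it, the mucositis item in Section 7.8.1 refers readers to it, and the sentence gives no B12 dose, so a site must look elsewhere to carry out the order. A pharmacist may well catch the figure. This lowers the risk but does not correct the printed order.

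Finally, a µg misread as mg would recur in a repeated sentence, so the two occurrences are not fully independent. That possibility cannot be excluded completely, but the micro-units preserved elsewhere make it unlikely.

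**Conclusion.** The concern holds, with medium confidence. The protocol orders a gram of folic acid daily for all pralatrexate recipients in two places and gives no other dose. The amount is implausible for the stated prophylactic purpose: 28 g per cycle without a hold, about 42 to 49 times the printed leucovorin total.

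That implausibility rests on the scale and stated purpose of doses within the protocol. The explanation that mg was written for mcg is an assumption, and the 1,000-fold overstatement depends on it. The correct dose cannot be settled without the insert. This is a safety correction to the treatment text that should be made. It has no shown consequence for DLT rates, the CRM or partial-order CRM allocation, or the sample size.

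**What to change.** - Check the folic acid number and unit against the package insert that both sections cite.
- Print the verified dose and unit identically in Sections 5.2.2 and 6.2.
- Notify sites, so that new participants and those still receiving pralatrexate in Arms A and B are covered.

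This review does not propose the dose itself; that should come from the insert.

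The cost is one look-up, a wording correction in two places and a site notice. No data, visits or participants are added, and the design and analysis are unchanged.
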